**Control Arm (Arm B): Ifosfamide + Etoposide**

Ifosfamide 3000 mg/m^2/day, IV, daily for 3 consecutive days (Day 1 to 3), every 21 days, for a maximum of 5 cycles.

Etoposide 100 mg/m^2/day, IV, daily for 3 consecutive days (Day 1 to 3), every 21 days, for a maximum of 5 cycles.

Before dose administration on Day 1 of each cycle and prior to a change in dose due to dose reduction, the amount of lenvatinib needed for each subject must be calculated as follows:

$$\text{Scheduled dose (mg/m}^2\text{)} \times \text{body surface area (BSA) (m}^2\text{)} = \text{lenvatinib dose (mg)}$$

Body surface area (BSA) will be calculated using the method that is accepted and customarily used by the clinical site. BSA must be calculated on Day 1 of each cycle based on the subject's current height and body weight. BSA will be used to determine the amount of lenvatinib for each subject. BSA should not be corrected for amputation. The dose should be rounded to the nearest whole number. After adjustment for BSA, the daily dose of lenvatinib should not exceed 24 mg daily.

Subjects will receive study treatment as continuous 21-day cycles in both treatment arms. Treatment cycles will be counted continuously regardless of dose interruptions. If chemotherapy administration is precluded on Day 1 of a treatment cycle, the subject may resume treatment once recovered at the discretion of investigator. Subsequent chemotherapy will be administered every 21 ( $\pm 1$ ) days starting from the timepoint it was resumed.

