Disease progression per RECIST 1.1 during the randomization phase must be confirmed by IIR prior to the investigator discontinuing study treatment for a subject. In the event that the investigator considers alternative treatments must be instituted immediately for management of urgent medical complications of PD, study drugs may be discontinued without waiting for independent confirmation of radiographic evidence of PD. Subjects who discontinue study treatment without PD will continue to undergo tumor assessments according to the schedule until PD is documented or another anticancer therapy is initiated. If possible, before discontinuation of the subject from the study, the investigator should consult with the sponsor.

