### **During Post-treatment Follow-up**

Subjects who discontinue treatment without PD will have tumor assessments performed as per the appropriate tumor assessment schedule) or sooner if clinically indicated, for documented PD or until another anticancer therapy is initiated, whichever occurs first.

After data cutoff for PFS-1y and OS-1y analysis, tumor assessments may be performed as clinically indicated as per the institutional guidelines, following the prevailing local standard of care. All subjects will be followed for survival for 2 years after end of treatment or until death, unless the study is terminated by the sponsor, or the subject discontinues due to withdrawal of consent, or is lost to follow-up.

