- p. Subjects randomized to Arm A will continue to receive lenvatinib only after completion of 5 cycles with lenvatinib+ifosfamide+etoposide until progressive disease, unacceptable toxicity, subject request, study termination by the sponsor, subject noncompliance with safety or efficacy assessments, or withdrawal of consent. Subjects randomized to Arm B will be off-treatment after 5 cycles of ifosfamide+etoposide.
- q. All subjects who receive suspension formulation, with the exception of subjects using a nasogastric or gastrostomy tube, must complete the Palatability Questionnaire according to the Schedule of Assessments. If the subject is unable to complete the questionnaire this must be done by their parents or their legal guardian.
- r. **Screening:** Tumor assessments of the chest, abdomen, pelvis, and other areas of known disease or newly suspected disease should be performed within 28 days prior to C1D1. Scans of the abdomen, pelvis, and other areas of the body may be done with MRI instead of CT, but evaluation of the chest should be done with CT. CT scans should be performed with oral and iodinated IV contrast and MRI scans should be performed with IV gadolinium chelate.

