**Table 5 Schedule of Assessments in Study E7080-G000-230 – Randomization Phase**

Phase	Prerandomization		Randomization a (All cycles are 21 days in duration)																	
	Screening b	Baseline c	Treatment d																Off-Tx	Follow-up e
Period	1	2	3	4	5	6	7	8	9	10	11	12	13	14	15	16	17	18+		
Visit	1	2	3	4	5	6	7	8	9	10	11	12	13	14	15	16	17	18+		
Cycle			Cycle 1			Cycle 2			Cycle 3			Cycle 4			Cycle 5			Cycle 6-X		
Day	-28 to -2	-1	1	8	15	1	8	15	1	8	15	1	8	15	1	8	15	1		
Procedures/Assessments																				

**Treatment Phase:** Tumor assessments of the chest, and other areas of known disease at Screening or newly suspected disease should be performed every  $6\pm 1$  weeks from C1D1 until Week  $18\pm 1$  week, then every  $9\pm 1$  weeks until Week  $54\pm 1$  week, and thereafter, every  $12\pm 2$  weeks until documentation of PD during the Treatment Phase (or sooner if there is evidence of progressive disease) and should utilize the same methodology (CT or MRI) and scan acquisition techniques (including use or nonuse of IV contrast) as was used for the screening assessments. Tumor response will be assessed according to RECIST 1.1. Subjects who discontinue must complete the off-treatment tumor assessment. Any CR or PR must be confirmed not less than 4 weeks following the initial achievement of the response. After treatment discontinuation, tumor assessment should continue to be performed according to the schedule: every  $6\pm 1$  weeks until Week  $18\pm 1$  week, then every  $9\pm 1$  weeks until Week  $54\pm 1$  week, thereafter, to be performed every  $12\pm 2$  weeks until documentation of progression or start of a new anticancer agent.

- s. Brain CT with contrast or MRI pre- and post- gadolinium contrast will be performed at the Screening Visit as clinically indicated, and thereafter during treatment as clinically indicated. For subjects with protocol-eligible treated brain metastases, brain CT/MRI will be performed at all tumor assessment time points.

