#### 8.7.1.6.2 SECONDARY EFFICACY ANALYSES

PFS-1y rate will be analyzed using the same methods as the primary efficacy analysis. PFS censoring rules will follow FDA guidance of 2007, however, removal of baseline lesions after completion of Week 18 without progression is not a trigger for PFS censoring after 18 weeks. (refer to [Section 8.4.7.3](#) for allowed concomitant treatments/procedure in the study).

Overall survival (OS) will be compared between treatment arm and control arm using the stratified logrank test with time to first relapse/refractory disease (early [ $<18$  months] or late [ $\geq 18$  months]) and age ( $<18$  or  $\geq 18$  years) as strata. Median OS with 2-sided 80% and 95% CIs will be calculated using K-M product-limit estimates for each treatment arm, and the K-M estimates of OS will be plotted over time. The Cox regression model will be used to estimate the hazard ratio and its 80% and 95% CIs stratified by time to first relapse/refractory disease (early [ $<18$  months] or late [ $\geq 18$  months]) and age ( $<18$  or  $\geq 18$  years). Kaplan-Meier (K-M) estimates will also be presented for 4, 6, 9 and 12 months with 2-sided 80% and 95% CIs.

Overall PFS will be analyzed similarly to OS. Median PFS and 2-sided 80% and 95% (as exploratory) CIs will be presented, and the K-M estimates of PFS will be plotted over time. The Cox regression model will be used to estimate the hazard ratio and its 80% and 95% CIs stratified by time to first relapse/refractory disease (early [ $<18$  months] or late [ $\geq 18$  months]) and age ( $<18$  or  $\geq 18$  years). K-M estimates will also be presented for 4, 6, 9, and 12 months with 2-sided 80% and 95% CIs.

The ORR will be compared between the test and control groups using either a chi-square test or a Cochran-Mantel-Haenszel test stratified by time to first relapse/refractory disease (early [ $<18$  months] or late [ $\geq 18$  months]) and age ( $<18$  or  $\geq 18$  years), as appropriate. Corresponding odds ratios and their 2-sided 80% and 95% CIs comparing the groups will also be presented. The individual treatment group ORRs will also be calculated along with exact 95% confidence intervals using the Clopper and Pearson method.

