#### 8.1.2.1 Treatment Period

The Treatment Period for each subject will begin at the time of randomization and will end at the completion of the Off-Treatment Visit which will occur within 30 days after the final dose of study treatment.

Subjects will receive study treatment as continuous 21-day cycles in both treatment arms. Treatment cycles will be counted continuously regardless of dose interruptions. If chemotherapy administration is precluded on Day 1 of a treatment cycle, the subject may resume treatment once recovered at the discretion of investigator. Subsequent chemotherapy will be administered every 21 ( $\pm 1$ ) days starting from the timepoint it was resumed. Subjects will undergo safety and efficacy assessments as defined in the Schedule of Procedures/Assessments ([Table 5](#)). Subjects randomized to Arm A will continue to receive lenvatinib until disease progression (PD) confirmed by IIR, development of unacceptable toxicity, subject request, withdrawal of consent, or study termination by the sponsor, whichever occurs first.

Disease progression (PD) must be confirmed by IIR prior to the investigator discontinuing study treatment for a subject. In situations where the investigator judges that alternative treatments must be instituted immediately for a subject's safety, study drugs may be discontinued without waiting for IIR confirmation of radiographic evidence of PD. If possible, before discontinuation of the subject from the study, the investigator should consult with the sponsor.

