#### 8.1.2.2 Follow-Up Period

The Follow-up Period begins the day after the Off-Treatment Visit and will continue as long as the subject is alive, unless the subject withdraws consent or the sponsor terminates the study.

Subjects may at any time withdraw consent for further study participation. No further data will be collected on subjects once consent has been withdrawn, however, an investigator may consult public records to establish survival status if permitted by local regulations.

All adverse events (AEs) will be captured for 30 days after the last dose of study drug.

All subjects who discontinue study treatment early for reasons other than PD, will continue to undergo tumor assessments every 6 weeks until Week 18, then every 9 weeks until Week 54, thereafter, every 12 weeks until IIR confirmation of radiographic evidence of PD as described in the tumor assessments in the assessment schedule, or until another anticancer therapy is initiated.

Subjects in both Arm A and Arm B will be followed for survival every 12 weeks ( $\pm 1$  week) and all subsequent anticancer treatments received will be recorded. Subjects who are being followed for survival at the time of data cutoff for the PFS-1y and OS-1y analysis (ie, at the end of the Randomization Phase) will continue to be followed for survival during the Follow-up Period of the Extension Phase.

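### The rule that IIR confirm progression acts only on stopping study treatment, and the off-treatment imaging stop rules conflict, so PFS-1y and PFS by IIR risk arm-dependent censoring

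*Protocol*

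**What the plan says.** Section 8.5.1.2.1 (During Treatment Phase) states that "Disease progression per RECIST 1.1 during the randomization phase must be confirmed by IIR prior to the investigator discontinuing study treatment for a subject". The synopsis and Section 8.1.2.1 carry the same requirement, with an exception for urgent situations.

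Treatment lasts differently in the two arms. Table 5 says "Subjects randomized to Arm B will be off-treatment after 5 cycles of ifosfamide+etoposide". Section 8.1.2.1 says "Subjects randomized to Arm A will continue to receive lenvatinib until disease progression (PD) confirmed by IIR", subject to the usual other reasons for stopping.

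For subjects off treatment, imaging ends on different terms in different places:

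- Section 8.1.2.2 (likewise the synopsis, Study Design) scans "until IIR confirmation of radiographic evidence of PD" or until another anticancer therapy starts. It covers subjects who stop treatment early for reasons other than PD.
- Section 8.5.1.2.1 (During Post-treatment Follow-up) scans "for documented PD or until another anticancer therapy is initiated, whichever occurs first".
- The tumor-assessment footnote of Table 5 scans "until documentation of progression or start of a new anticancer agent".
- Sections 8.3.3 and 8.5.5 and the synopsis (Efficacy Assessments) also end at documented PD or new therapy, without naming IIR.

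On analysis, Section 8.7.1.6.2 says "PFS censoring rules will follow FDA guidance of 2007". Section 8.4.7.2 and the synopsis say that added antitumor therapy while on study is judged to be evidence of progression.

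**The concern.** The trial is open label, and Section 8.2 relies on central blinded reading to keep bias out of the efficacy comparison. That protection needs both arms to be followed to IIR progression on the same terms.

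The explicit confirmation rule is attached to one act, stopping study treatment. An Arm B subject who has completed five cycles has no study treatment to stop. If that subject is called PD locally but not by IIR, the text of Section 8.5.1.2.1 or Table 5 lets imaging end, either on the local call or when new therapy starts, with no IIR event recorded. An Arm A subject on lenvatinib in the same position is still under the rule and continues to be scanned.

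Subjects called PD locally are likely to be the ones closest to IIR progression. Losing them as censored observations mainly in one arm is informative censoring. It would affect PFS-1y, the PFS hazard ratio and median PFS.

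**Working it through.** **Timeline.** The cycle length comes from Section 8.4.1 (21 days) and the scan weeks from Section 8.5.1.2.1.

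- Last Arm B dose: 4 × 21 + 3 = Day 87. End of Cycle 5: 5 × 21 = Day 105 (Week 15).
- Four months: 365.25 / 3 = Day 121.75 (Week 17.4). One year: Week 52.2.
- The rule has nothing to act on in Arm B for 52.2 − 15 = 37.2 weeks, or 71% of the PFS-1y window.
- Scans before Day 121.75 are at Weeks 6 and 12 (Days 42 and 84), both before the last Arm B dose. The Week 18 scan is nominally Day 126; its window opens on Day 119.

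**Illustrative size.** The documents give no rate of disagreement between local and central reading, so q below is an assumption. The model is:

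- true PFS is exponential and equal in both arms;
- IIR PD is dated at the first scheduled scan after true progression;
- a share q is called PD locally one scan earlier;
- in Arm B, if that earlier scan is after Day 87, the subject starts new therapy at once and is censored there;
- Arm A has no such loss.

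Let h be the chance of progression in one 9-week interval. At each of the scans at Weeks 27, 36 and 45, the events fall from h to h(1 − q) and the risk set falls from 1 to 1 − qh. The apparent survival factor is therefore (1 − h)/(1 − qh). The Kaplan-Meier (K-M) estimate at one year, whose last scan is Week 45, becomes

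observed PFS-1y = S(Week 45) / (1 − qh)³.

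Example with a 6-month median: the rate is ln 2 / 182.6 = 0.003796 per day, so h = 1 − exp(−0.003796 × 63) = 0.2127 and S(315 days) = 0.3025. At q = 30%: 0.3025 / (1 − 0.0638)³ = 0.3025 / 0.8206 = 36.9%, an overstatement of 6.6 points.

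| Median PFS | Arm A (no loss) | Arm B, q = 10% | q = 20% | q = 30% |
|---|---|---|---|---|
| 2 months | 2.8% | 3.2% | 3.8% | 4.6% |
| 4 months | 16.6% | 18.2% | 20.1% | 22.1% |
| 6 months | 30.3% | 32.3% | 34.5% | 36.9% |
| 9 months | 45.1% | 47.1% | 49.3% | 51.6% |

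A simulation on the same schedule agrees to within 0.1 point. The 2-month row matters because the protocol's control assumption in Section 8.7.2, 25% at 4 months, means a median of 4 × ln 2 / ln 4 = 2 months under this model.

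**How many subjects.** The number censored by one year is 36 × q × [S(Week 18) − S(Week 54)]. At q = 30%:

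- 2-month median: 36 × 0.3 × (0.238 − 0.014) = 2.4
- 4-month median: 36 × 0.3 × (0.488 − 0.116) = 4.0
- 6-month median: 36 × 0.3 × (0.620 − 0.238) = 4.1
- 9-month median: 36 × 0.3 × (0.727 − 0.384) = 3.7

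**Primary endpoint.** No scan at which the model can censor falls before Day 121.75, so the K-M PFS-4m estimate does not move at any q.

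**The case against.** A reader might infer that nothing requires IIR agreement in Arm B after Cycle 5. The documents do not support that. Section 8.5.1.2.1 sends every scan to the core laboratory for efficacy assessment and confirmation of PD, without limit by arm. Section 8.3.3 says that IIR confirmation is no longer required after the data cutoff, which makes sense only if it is expected before then. What stands is that this expectation is implied, while several operative stop rules say something weaker. The conflict lies within the one complete protocol text in the file, so it is not a difference between versions.

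Censoring at new therapy is also not certain. If the statement in Section 8.4.7.2 governs, added therapy would count as progression, and the subject would be an event. Section 8.7.1.6.2 instead points to external censoring rules. The protocol does not say which applies to PFS by IIR.

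The model leans towards a larger effect. It assumes that every early local call leads at once to new therapy; if half do (6-month median, q = 30%), the shift is about 3 points. It also sets the Arm A loss to zero. Arm A subjects who stop for toxicity, or under the urgent exception, leave the rule too, and Section 6.3.1 reports that 25.8% discontinued this combination because of TEAEs. Only disagreement with the local call first is modelled; other patterns could change the direction.

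None of this removes the asymmetry between Arm B completers and Arm A subjects on lenvatinib. Nor can a later analysis plan recover scans that were never taken.

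**Conclusion.** The point holds for the secondary endpoints. Arm B completers fall outside the explicit confirmation rule, and the off-treatment stop rules contradict each other. This gives Arm B an easier exit from imaging without an IIR event. Under the assumptions above, with q from 10% to 30%, Arm B PFS-1y is overstated by about 0.5–2 points at a 2-month median and about 2–7 points at medians of 4–9 months. About 4 of 36 Arm B subjects or fewer are censored in this way by one year.

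Three stronger readings should be avoided:

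- *The primary endpoint is biased.* The exposed gap runs only from Week 15 to Week 17.4, and only a Week 18 scan taken early could fall in it. PFS-4m is essentially unaffected.
- *Five to eight Arm B subjects are lost.* That count (15–22% of 36 at q = 30%, medians 4–9 months) covers all follow-up, not the first year.
- *The flaw flatters lenvatinib.* In this model it works against lenvatinib, so the risk is a masked benefit.

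The true size is unknown because no discordance rate is given.

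**What to change.** Apply one imaging stop rule, IIR-confirmed PD, up to data cutoff to all off-treatment subjects in both arms, including Arm B completers. To do this:

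- In Section 8.1.2.2 and the synopsis (Study Design), delete the restriction to subjects who stop early.
- Align Sections 8.3.3, 8.5.1.2.1 and 8.5.5, the Table 5 footnote and the synopsis (Efficacy Assessments) with that rule. A local call or a new therapy would then not by itself end scanning. Changing only documented PD to IIR-confirmed PD would leave the new-therapy exit open.
- Send any local PD call in an off-treatment subject for IIR reading when it is made, keeping the existing urgent exception. This concerns imaging only and does not dictate when new therapy may start.
- Reconcile Section 8.4.7.2 and the synopsis with Section 8.7.1.6.2, so that the handling of new anticancer therapy in PFS by IIR is stated once.
- Report by arm the number with local PD but no IIR PD and the number censored at new therapy. Add a sensitivity analysis counting new anticancer therapy, or local PD, as an event.

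The cost is protocol wording, a modest number of quicker central reads of scans that already go to the core laboratory, and some further scheduled scans in discordant subjects.

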### **During Post-treatment Follow-up**

Subjects who discontinue treatment without PD will have tumor assessments performed as per the appropriate tumor assessment schedule) or sooner if clinically indicated, for documented PD or until another anticancer therapy is initiated, whichever occurs first.

After data cutoff for PFS-1y and OS-1y analysis, tumor assessments may be performed as clinically indicated as per the institutional guidelines, following the prevailing local standard of care. All subjects will be followed for survival for 2 years after end of treatment or until death, unless the study is terminated by the sponsor, or the subject discontinues due to withdrawal of consent, or is lost to follow-up.

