- t. Height will be assessed at the Baseline Visit, Day 1 of every 4 cycles during the Treatment Phase, at the Off-treatment Visit and every 3 months during the Post-treatment Follow-up. Proximal tibial growth plates x-rays should be conducted at baseline and at the Off-treatment Visit. If the growth plates are closed at baseline then the subject does not need a reassessment at the Off-treatment Visit. Tibial growth plate x-rays will be optional for Germany.
- u. Tanner Stage will be assessed at the Baseline Visit, at the Off-treatment Visit, and annually thereafter during the Post-treatment Follow-up.
- v. Blood samples will be collected only from subjects in Arm A at the Baseline Visit, C1D15, Day 1 of Cycles 2, 4, and 6, for assessment for blood serum sample to measure factors implicated in angiogenesis.
- w. An archival tumor sample from the most recent surgery or biopsy for identification of predictive biomarkers and pathology review may be collected from subjects in Arm A at any time during the study, unless no such material is available.
- x. Survival data will be collected every 3 months until death as per the protocol. All anticancer therapies will be collected.
- y. Concomitant medications will be recorded throughout the study and for 30 days after last dose. All anticancer therapy will be recorded until time of death or termination of Survival Follow-up.
- z. AEs will be recorded from the date of signed informed consent, throughout the study, and for 30 days after last dose. SAEs irrespective of relationship to study treatment must be reported as soon as possible but not later than 24 hours.

**Table 6** presents the Schedule of Procedures/Assessments for the Extension Phase of the study.

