### 8.7.1.6 Efficacy Analyses

Efficacy analyses will be based primarily on the Full Analysis Set.

All the statistical analysis will be conducted at the PFS-1y/OS-1y analysis data cutoff date (ie, when the last subject has completed 18 cycles of treatment or discontinues before the end of Cycle 18, whichever occurs first), including the analysis of PFS-4m rate. Additional follow-up analysis will be based on the date of data cutoff for the additional follow-up analysis for OS or at the time of last subject last visit, whichever occurs later.

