#### 8.1.3.2 Follow-Up Period

The Follow-up Period will begin the day after the Off-Treatment Visit and will last until death or for 2 years after end of treatment for a subject, unless the study is terminated by the sponsor, or the subject discontinues due to withdrawal of consent, or is lost to follow-up. Subjects will be treated by the investigator according to the prevailing local standard of care. Subjects will be followed every 12 weeks ( $\pm 1$  week) for survival and all subsequent anticancer treatments received will be recorded.

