### 8.3.3 Removal of Subjects From Therapy or Assessment

Subjects will continue to receive study treatment until any of the following occur:

- Progressive disease (as confirmed by IIR)
- Unacceptable toxicity
- Subject request
- Withdrawal of consent
- Termination of the study by the Sponsor

The investigator may discontinue treating a subject with study treatment or withdraw the subject from the study at any time for safety or administrative reasons. The subject may decide to discontinue study treatment or withdraw from the study at any time for any reason. The reason for discontinuation will be documented. If a subject discontinues study treatment, the subject will enter the Follow-Up Period and complete protocol-specified off-treatment visits, procedures, and survival follow-up unless the subject withdraws consent. The investigator should confirm whether a subject will withdraw from study treatment but agree to continue protocol-specified, off-treatment study visits, procedures, and survival follow-up, or whether the subject will withdraw consent. If a subject withdraws consent, the date will be documented in the source documents.

During the Follow-Up Period, subjects who have discontinued study treatment without progression should have disease assessments as per the appropriate tumor assessment schedule in [Table 5](#) and [Table 6](#) from the date of the last assessment until PD is documented or another anticancer therapy is initiated. After data cutoff of PFS-1y and OS-1y, tumor assessments may be performed as clinically indicated per institutional guidelines, following the prevailing local standard of care, and IIR confirmation of radiographic evidence of PD will not be required.

All subjects will be followed for survival until death or for 2 years after end of treatment for a subject, except where a subject withdraws consent or the sponsor chooses to halt survival follow-up after completion of the primary study analysis.

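### Survival follow-up runs to death in some places and to 2 years after end of treatment in others, and the second rule stops overall survival follow-up at different times in the two arms

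*Protocol*

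**What the plan says.** Rule 1, to death:

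- Section 8.1.2.2 (Randomization Phase, repeated in the synopsis): the Follow-up Period "will continue as long as the subject is alive, unless the subject withdraws consent or the sponsor terminates the study".
- Table 5, survival footnote: "Survival data will be collected every 3 months until death as per the protocol". Table 6, the schedule for the Extension Phase, carries the same footnote.

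Rule 2, to death or 2 years after end of treatment:

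- Section 8.5.1.2.1, During Post-treatment Follow-up: "All subjects will be followed for survival for 2 years after end of treatment or until death".
- Section 8.3.3: "All subjects will be followed for survival until death or for 2 years after end of treatment for a subject". The exceptions are withdrawal of consent and a sponsor decision to stop survival follow-up once the primary study analysis is complete.
- Section 8.1.3.2 (Extension Phase, repeated in the synopsis): follow-up "will last until death or for 2 years after end of treatment for a subject".

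Treatment length differs by design. Arm B chemotherapy is given "daily for 3 consecutive days (Day 1 to 3), every 21 days, for a maximum of 5 cycles". Arm A continues lenvatinib until progression confirmed by independent review, unacceptable toxicity, subject request, withdrawal of consent or study termination (section 8.1.2.1).

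OS is a secondary endpoint, compared by stratified logrank test and Cox model (section 8.7.1.6.2). Section 8.7.1.6 plans a later look as well: "Additional follow-up analysis will be based on the date of data cutoff for the additional follow-up analysis for OS".

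**The concern.** A site with a living subject who is 2 years past the last dose cannot tell from the protocol whether to keep calling.

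If it follows Rule 2, the length of survival follow-up depends on how long the subject was treated. That depends on the arm and, within Arm A, largely on when the subject progressed. Arm A subjects who progress early leave the risk set first, so the late part of the Arm A curve rests on those who were treated longest. Follow-up of Arm B ends earlier, and more of its late deaths go unrecorded. Once contact has ended, those data are hard to recover, and the trial has only 36 subjects per arm.

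**Working it through.** **Can the rules be reconciled by phase?** The candidate reading is: to death before the PFS-1y/OS-1y data cutoff, 2-year limit after it. It fits sections 8.1.2.2 and 8.1.3.2, and section 8.1.2.2 does pass subjects in survival follow-up on to the Extension Phase. Two things do not fit. Sections 8.3.3 and 8.5.1.2.1 apply the limit to all subjects, and the Extension Phase's own schedule (Table 6) says until death.

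**Where the 2-year limit falls.** Limit = months on treatment + 24, with 30.4375 days per month, counted from Cycle 1 Day 1.

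| Subject | End of treatment | Limit (months) |
|---|---|---|
| Arm B, last scheduled dose Cycle 5 Day 3 | 4 × 21 + 3 = Day 87 (2.9 months) | 26.9 |
| Arm B, end of Cycle 5 | Day 105 | 27.4 |
| Arm B, latest Off-Treatment Visit | 87 + 30 = Day 117 | 27.8 |
| Arm A, progression at Week 6 | Day 42 | 25.4 |
| Arm A, progression at Week 18 | Day 126 | 28.1 |
| Arm A, progression at 11.1 months (median PFS of the earlier combination cohort, section 6.3.1, used as an assumption) | 11.1 months | 35.1 |
| Arm A, stops at end of Cycle 18 | 18 × 21 = Day 378 (12.4 months) | 36.4 |

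The gap for an Arm A subject treated for 11 to 12 months is 35.1 − 26.9 = 8.2 to 36.4 − 26.9 = 9.5 months.

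**Can the limit bind before the main cutoff?** With the stated study period of about 36 months and 12.4 months for the last subject's 18 cycles, accrual spans about 36 − 12.4 = 23.6 months. Arm B subjects entered in the first 36 − 26.9 = 9.1 months could reach the limit before the cutoff if they are still alive.

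**Effect on OS.** The calculations are simulations. Inputs that are not in the protocol are assumptions: uniform entry over 23.6 months, 36 per arm, exponential PFS with medians 8 (A) and 4 (B) months, and exponential post-progression survival. Treatment ends at progression in Arm A, and at progression or Day 87, whichever is earlier, in Arm B. The 50-month analysis date is also assumed, since the protocol fixes none. Post-progression medians tried: 8 months, and 16.3 − 11.1 = 5.2 months from the earlier cohort's median OS and PFS.

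| Analysis at 50 months | Deaths without limit (A / B) | Deaths with limit (A / B) | Loss (A / B) |
|---|---|---|---|
| Post-progression median 8 | 29.8 / 33.0 | 28.3 / 29.1 | 1.5/29.8 = 5% / 3.9/33.0 = 12% |
| Post-progression median 5.2 | 32.2 / 34.9 | 31.5 / 32.7 | 0.7/32.2 = 2% / 2.2/34.9 = 6% |

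With the 8-month median the hazard ratio moves from 0.665 to 0.648, and from 0.747 to 0.729 if prognosis is correlated (frailty variance 0.5). Power changes by 1 to 2 points. At a 36-month cutoff, if the limit applies before the cutoff, about 1 Arm B death is lost and the hazard ratio moves from 0.644 to 0.639. If the limit binds only after a 36-month cutoff, nothing is lost at that cutoff. In the 5.2-month case at 50 months, Arm B then has 33.2 deaths instead of 32.7.

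**Type I error.** These runs used identical outcomes in both arms, median PFS 4 to 11.1 months, post-progression median 8 to 14 months, a 36-month cutoff and 1,500 replicates. The one-sided 10% logrank test rejected in 9.4-9.8% of trials with the limit and 9.0-10.1% without it. The simulation error is √(0.1 × 0.9/1500) = 0.8 points, so no inflation is visible. The limit ended follow-up for about 4 to 6 living Arm B subjects and about 1 to 3 in Arm A.

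**The case against.** The strongest reply is that the conflict is mostly the phase structure. In section 8.5.1.2.1 the 2-year sentence comes directly after one about the period following the data cutoff, section 8.3.3 has the same order, and the table footnotes defer to the protocol text. Section 8.7.1.6 places the main analyses at that cutoff, so on this reading they lose nothing. This stands as far as it goes, but Table 6 and the all-subjects wording remain unexplained, and the additional OS analysis is exposed on either reading.

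Other points that stand:

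- Day 87 is nominal, because chemotherapy may be delayed and end of treatment is not defined for this purpose. A reader might infer that no Arm B subject can be followed past 27 months. That is true only of on-schedule subjects.
- Arm A can also stop for toxicity or on request. In the earlier combination cohort 25.8% stopped for adverse events. Early progressors stop at similar times in both arms.
- A reader might infer that OS has no censoring rule for subjects whose follow-up the limit ends. The definition does not name them, but censoring at the date last known alive covers them in practice.
- Section 8.3.3 already lets the sponsor halt survival follow-up after the primary analysis. That power is optional and does not settle which rule sites follow until then.

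**Conclusion.** The inconsistency is real, and the 2-year limit gives follow-up lengths that depend on arm and, in Arm A, on progression time. The consequence is modest: unequal loss of late OS data, with about 1 Arm B death lost at a 36-month cutoff if the limit applies before it, and about 6-12% of Arm B deaths against 2-5% of Arm A deaths at an assumed 50-month analysis. In the 8-month scenarios the hazard ratio shift of about 0.02 favours the test arm. A longer post-progression survival would enlarge the loss.

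A reader might go further and conclude that the OS test is invalid or that the primary result is affected. The documents do not support either. The limit never falls earlier than 24 months after treatment ends, so it cannot touch PFS-4m, PFS-1y, OS-1y or the Kaplan-Meier estimates planned at 4, 6, 9 and 12 months. No type I error inflation was seen. This is a cheap improvement, not a flaw in the main analysis.

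**What to change.** Align section 8.5.1.2.1 (During Post-treatment Follow-up), section 8.1.3.2 with its synopsis counterpart, and section 8.3.3 with section 8.1.2.2 and the table footnotes. All subjects in both arms would be contacted for survival every 12 weeks until death, withdrawal of consent, loss to follow-up or one common calendar date, the OS data cutoff. The sponsor can set that date under its existing right to halt follow-up. If a fixed length is preferred, count it from randomization and not from end of treatment.

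The cost is a wording change and a few extra 12-weekly survival contacts, mostly for long-surviving Arm B subjects. No visits or scans are added.
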